6.3.4.3 Quality of Life Assessment: SF-36 Questionnaire Total Score

The SF-36 Health Survey is a self-administered, 36-item questionnaire designed to measure 8 domains of functional health status and well-being. For this study, the questionnaire data is collected at baseline, week 26 and week 52. The SF-36 instrument guidelines will be used to assess and summarize the overall health status. The SF-36 consists of 8 scaled scores with range 0-100 with higher score indicating better health. The 8 sections or domains are:

- Vitality
- Physical functioning
- Bodily Pain
- General Health Perceptions
- Physical Role Functioning
- Emotional Role Functioning
- Social Role Functioning
- Mental Health

There are also two component scores. The Physical Component Summary Score is a composite of the Physical Functioning, Role Functioning, Bodily Pain and General Health scales. The Mental

Health Component Summary Score is a composite of the Vitality, Social Functioning, Role-Emotional and Mental Health scales.

All above-mentioned domain and component scores will be provided by QualityMetric and will be presented for data listings.

6.3.4.4 Inflammatory Bowel Disease Questionnaire (IBDQ) Score

IBDQ is used to assess IBD status. IBDQ is a valid and reliable quality of life instrument that incorporates social, systemic and emotional symptoms together with bowel-related symptoms into activity index. The IBDQ includes 32 questions on 4 areas of health-related quality of life:

Bowel Systems (10 questions: 1, 5, 9, 13, 17, 20, 22, 24, 26, 29),
Emotional Health Function (12 questions: 3, 7, 11, 15, 19, 21, 23, 25, 27, 30, 31, 32),
Social Function (5 questions: 4, 8, 12, 16, 28), and
System Function (5 questions: 2, 6, 10, 14, 18). Each item is rated on 7-point Likert scale (higher scores equate to higher quality of life).

A total IBDQ score is calculated as sum of all 32 scores and the total ranges from 32 to 224. If more than 4 questions are missing, then total scores will not be calculated. If 4 or fewer questions are missing, then missing questions will be imputed by the mean of the rest of available question scores.

Summary descriptive statistics including number of observations, mean with 95% CI, standard deviation, median, inter-quartile ranges, minimum, and maximum will be presented in tables and bar graph for the actual and change from baseline scores for IBDQ total score by scheduled visits (week 16 and week 52). The summaries will be done by parent study treatment and overall.

6.3.4.5 Serum Marker of Inflammation: C-reactive Protein (CRP)

The CRP is used as marker of inflammation. The CRP level data collected at baseline, week 16, 26, 39 and 52 will be used to assess inflammation at baseline and at different visits post-baseline. Summary descriptive statistics for the actual observed and change from baseline will include mean with 95% CI, standard deviation, median, inter-quartile ranges and range for each parent study treatment and overall by visit.

In addition, the CRP level will be classified into two categories: “Normal (≤ 0.999 mg/dL)” and “High (> 0.999 mg/dL)”. Summary results will show number of patients and proportion (%) along with 95% exact Clopper-Pearson CI with “Normal level” and with “High Level” by parent study treatment group and overall by visit. Shift tables from baseline to each post baseline visit will also be presented.

6.3.4.6 Stool Marker of Inflammation: Fecal calprotectin

The fecal calprotectin is used as marker of inflammation. The level of fecal calprotectin data collected at different visits will be used to assess inflammation at baseline and at different visits post-baseline (weeks 16, 26 and 52). Summary descriptive statistics for the actual observed and

change from baseline will include mean with 95% CI, standard deviation, median, inter-quartile ranges and range for each parent study treatment group and overall by visit.

In addition, fecal calprotectin will be classified into two categories: “Normal (≤ 162.9 mcg/g)” and “High (> 162.9 mcg/g)”. Summary results will show number of patients and proportion (%) along with 95% exact Clopper-Pearson CI with “Normal level” and with “High Level” by treatment group by visit. In addition, shift tables from baseline to each post baseline visit will also be presented.

6.3.4.7 Additional Endpoints: CDAI score and PRO-2

PRO-2 is defined as $7 \times$ (mean daily number of liquid or very soft stools) + $7 \times$ (mean daily abdominal pain score) based on CDAI assessment. CDAI and PRO-2 scores will be summarized descriptively by visit.

6.4 Safety Analysis

All summarization of safety data will be based on the safety population by parent study treatment group and overall.

6.4.1 Adverse Events

Each verbatim adverse event (AE) term recorded during the study will be mapped to a system organ class and preferred term using the current MedDRA Dictionary.

A treatment-emergent AE (TEAE) is defined as an AE that based on start date information occurred after the first study drug administration or an AE that started before the first study drug administration but worsened in severity (i.e., became more severe) after administration of the study drug.

Treatment related adverse events will be defined as the adverse events for which the investigator indicates the relationship to study drug as possible, probable, or definite. If the relationship to study drug for an AE is not recorded, it will be assumed to be treatment related in the summary tables. Similarly, if severity of an AE is missing, the severity will be summarized as severe.

A by-subject listing of all AEs (including non-treatment-emergent AEs) will be provided and will include all AE data recorded on the eCRF. All summaries of AEs will present the number and percent of subjects reported events by system organ class and preferred term and by treatment group. If a subject has multiple occurrences of an AE, the subject will be counted only once in the respective AE.

For summaries of adverse events by maximum severity or maximum relationship, if a subject has multiple occurrences of an AE, the subject will be counted only once for the respective Preferred Term at the maximum severity or maximum relationship.

An overall summary table by treatment and overall of AEs, SAEs, TEAEs, Serious TEAEs, treatment-related TEAEs, treatment-related SAEs, TEAEs leading to study discontinuation and study deaths will be provided using number and % of subjects.

Summary tables by treatment and overall will be provided by SOC and preferred term for each of the following types of AEs:

- All Treatment emergent AEs
- Study Drug related treatment emergent AEs
- Treatment emergent AEs by maximum severity
- Treatment emergent AEs leading to study discontinuation
- Serious Treatment emergent AEs (SAEs)
- Treatment-related serious AEs
- Treatment emergent AEs leading to Death

The following listings will be provided:

- All AEs
- Treatment related AEs
- AEs leading to study discontinuation
- SAEs
- Deaths

All study deaths will be listed using date and cause of death along with autopsy results as entered on the Death CRF.

6.4.2 Laboratory Parameters

Laboratory assessments will include:

Biochemistry: total protein, gamma glutamyl transferase (GGT), lactate dehydrogenase (LDH), sodium, potassium, chloride, magnesium, glucose, total bilirubin, AST(SGOT), ALT(SGPT), alkaline phosphatase, amylase, albumin, BUN, calcium, creatinine, uric acid, HCO₃, total cholesterol, creatinine phosphokinase, and inorganic phosphorous.

Hematology: RBC count, hemoglobin, hematocrit, platelet count, WBC count, WBC differential.

Urinalysis: Pregnancy, pH (dipstick), specific gravity (dipstick), glucose (dipstick), protein (dipstick), ketones (dipstick), blood (dipstick), Nitrites, Leucocytes and sediment microscopy if indicated by the dipstick.

Laboratory results will be presented in listings in measured units and summaries in conventional units.

Continuous laboratory values will be summarized descriptively by treatment group over time for each visit and as change from baseline to each visit. Categorical laboratory values will be summarized as the number and percentages of subjects in each category by treatment group over time for visit.

Laboratory parameters will also be summarized in shift tables by treatment, to determine the number and percentage of subjects with measurements classified in a particular category at each post-baseline visit with reference to the same classification at baseline. Biochemistry and hematology parameters (which are continuous in nature) will use the classifications of low, normal, and high relative to normal ranges, whereas appropriate categories will be selected for urinalysis parameters (which are categorical in nature), for example, normal and abnormal.

Subjects missing a value at any time point will be excluded from the summary statistics for that time point. If a subject has more than one value at any time point, then the latest non missing value will be used for summarization. All values will be presented in the data listings.

Listings of all individual laboratory data, indicating any values out of the normal range will be produced. A listing of lab parameter values flagged as abnormal will also be provided.

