4.1.1 Study Visit Schedule

	Screening / Opt Screening / Visit Week 26 of RHB-104-01	Baseline Day 1 / Week 0 ²	Week 2	Week 4	Week 8	Week 16	Week 26	Week 39	Week 52	Week 56
Study Visit Window	(up to 21 days before BL if initial colonoscopy is performed)	Up to 21 days post SCR	± 3 days	± 3 days	± 7 days	± 7 days	± 7 days	± 7 days	± 7 days	± 7 days
Informed Consent	X									
Inclusion/ Exclusion Criteria Demography, Medical History	X	X								
Concomitant Medications Assessment		X ³	X	X	X	X	X	X	X	X
Vital Signs and Physical Exam.	X ¹	X	X	X	X	X	X	X	X	X
Adverse Event Assessments		X ³	X	X	X	X	X	X	X	
Diary Dispensing (AE/ConMed)		X	X	X	X	X	X	X	X	X
Steroid Status		X				X	X	X	X	X
CDAI assessment	X ¹				X	X	X	X	X	X
CDAI Diary Dispensing ⁴					X	X	X	X	X	
Subject Assessments: IBDQ and SF-36	X ¹					X	X		X	
Uveitis Assessment	X ¹		X	X	X	X	X	X	X	X
ECG ¹⁰	X ¹			X		X			X	X
Hematology and Biochemistry	X ¹		X	X	X	X	X	X	X	X
Urinalysis ¹¹	X ¹		X	X	X	X	X	X	X	X
C-Reactive Protein (CRP)	X ¹					X	X	X	X	
MAP Testing Blood (PCR) with Add'l Sample for Future Use	X ¹				X	X	X	X	X	X
MAP culture from blood	X ¹					X	X		X	
Fecal calprotectin	X ¹					X	X		X	
C. difficile Testing	X ¹						X		X	
Pregnancy Test Urine	X ¹	X	X	X	X	X	X	X	X	X
Optional Colonoscopy and CDEIS/SES-CD; store images		X ⁴				X ⁵			X ⁶	
IWRS Entry		X ⁷		X ⁸			X ⁹			
Study Drug Dispensing		X	X	X	X	X	X	X		
Dispensing of Drug Administration Instructions ¹²		X	X							
Drug Return & Accountability		X ¹³	X	X	X	X	X	X	X	
Review of stool sampling technique					X	X		X		
Telephone reminder of dose escalation		Day 7	Day 21							

¹ Procedure performed as part of RHB-104-01

² Baseline visit should be scheduled once the RHB-104-01 Wk26 / RHB-104-04 Screening CDAI score has been calculated (using RHB-104-01 Wk26 hematoctrit value).

³ Ongoing AEs/ConMeds from RHB-104-01 should be captured in RHB-104-04 eCRF (AEs & ConMeds for RHB-104-01 are captured in -01 eCRF up to day prior to -04 BL)

⁴ The colonoscopy must be performed on or before the Baseline or Week 0 Visit and must not interfere with CDAI data collection. If applicable, biopsies may be collected as part of the RHB-104-01 study.

⁵ In consenting subjects, colonoscopy must be performed up to 14 days after Visit Week 16.

⁶ In consenting subjects, colonoscopy must be performed a minimum of 8 days and a maximum of 20 days prior to visit Week 52.

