4.2 Dosage and Administration of Study Drug

The target dose of RHB-104 is 5 capsules administered bid. In order to reach this target with minimal adverse effects, subjects who received placebo during the RHB-104-01 study will be titrated up over the first 4 weeks of treatment, and the dose will remain stable thereafter. Subjects who received RHB-104 will continue to receive RHB-104. In order to maintain blinding in the RHB-104-01 study all subjects will receive 5 blinded capsules bid for the duration of the RHB-104-04 study as detailed below. The study drug will be taken with food. Subjects who fail dose escalation to 5 capsules bid will be considered treatment failures and withdrawn from the study.

Blinded bid Dose Titration and Maintenance Dosing in RHB-104-04 is

		RHB-104-04 START-UP KIT (Weeks 1-4)				MAINTENANCE KITS (Weeks 5-52)
		Weeks				
		1	2	3	4	5-52
BLINDED ACTIVE ARM (ACTIVE + ACTIVE)	RHB-104	Active Daily Dose (mg)				
	Clarithromycin	950mg	950mg	950mg	950mg	950mg
	Rifabutin	450mg	450mg	450mg	450mg	450mg
	Clofazimine	100mg	100mg	100mg	100mg	100mg

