6.1.2 Baseline Definition

For subject who received any dose of study drug, baseline is the last non-missing result prior to first dose including the data collected during the parent study for SES-CD, CDEIS, Calprotectin, CRP and all lab assessment. For subjects who are enrolled into this open-label study but never received any study drug, baseline is either assessment collected at baseline visit if available or screening visit or as specified otherwise.

For fecal calprotectin, the baseline is the last available assessment up to day 3.

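### No planned laboratory table gives the number of subjects whose ALT or AST rose well above the upper limit of normal at any time on treatment

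*SAP*

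**What the plan says.** AST and ALT are among the biochemistry parameters in SAP 6.4.2, which sets out these displays:

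- **Descriptive statistics** of observed values and of change from baseline at each visit (Table 14.3.4.1 in SAP 8.1). SAP 6.1.1 defines these as number of observations, mean, SD, median and range.
- **Shift tables** giving the "number and percentage of subjects with measurements classified in a particular category at each post-baseline visit" against baseline, where biochemistry parameters "will use the classifications of low, normal, and high relative to normal ranges" (Table 14.3.4.2).
- **Listings** of all individual values with out-of-range flags, and a separate listing of abnormal values.

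Repeated values are handled by this rule: "If a subject has more than one value at any time point, then the latest non missing value will be used for summarization".

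SAP 6.4 adds the breakdown: "All summarization of safety data will be based on the safety population by parent study treatment group and overall". SAP 4.1.1 schedules the row "Hematology and Biochemistry" at eight post-baseline visits (weeks 2, 4, 8, 16, 26, 39, 52 and 56). SAP 8.1 lists no biochemistry table other than the two above.

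The protocol synopsis names change from baseline in chemistry parameters as a safety outcome. Its exclusion criteria give AST or ALT above 2 x ULN as an example of a clinically significant abnormality at entry. The documents give no on-treatment threshold.

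**The concern.** For liver enzymes, a safety reader wants to know how many subjects rose well above ULN at any time on drug. That question is about each subject's worst value, and the planned tables are organised by visit.

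Three features keep the answer out of them. The High category begins just above ULN, so for a subject who starts normal, 1.05 and 10 x ULN fall in the same cell, and a rise from 1.5 to 8 x ULN counts as High to High. Visit counts cannot be added over eight visits, because the same subject may recur. The range shows that a high value occurred, not how many subjects had one.

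The latest-value rule is a separate matter. It is not the reason the count is missing, but it could also remove a peak from the maximum.

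At stake is the summary of a named safety outcome over up to 52 weeks of treatment. No efficacy estimate or test is affected.

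**Working it through.** **1. The plan's own figure.** The only design figure is the Clopper-Pearson width in SAP 6.1.7. For 50/100 the interval is 0.3983 to 0.6017, width 0.2034, which agrees with the stated 0.203. The point does not depend on it.

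**2. Inputs for the illustration.** From the SAP: 100 subjects, eight post-baseline draws, summaries by parent arm and overall. Assumed, because the documents do not say: 50 subjects per arm; 8 subjects starting at ALT 1.5 x ULN and 92 at 0.6; exactly one value of 8 x ULN at each visit. These values are chosen to make the ambiguity visible, not to be realistic.

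**3. All affected subjects in one arm.** At every visit the affected arm has:

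- mean = (42 x 0.6 + 7 x 1.5 + 8)/50 = 43.7/50 = 0.874; SD 1.0755; maximum 8.0
- mean change = 6.5/50 = 0.13; SD of change = 6.5/√50 = 0.919; maximum change 6.5
- High to High 8, Normal to Normal 42

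Overall, mean change is 0.065 and its SD 0.65. All of this is the same whether the eight high values come from 1, 2, 4 or 8 subjects.

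| Subjects above 3 x ULN | % | Exact 95% CI |
|---|---|---|
| 1/100 | 1.0 | 0.03 to 5.45 |
| 2/100 | 2.0 | 0.24 to 7.04 |
| 4/100 | 4.0 | 1.10 to 9.93 |
| 8/100 | 8.0 | 3.52 to 15.16 |

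**4. Where the information stops.** Within one visit the statistics can be quite informative. Remove the maximum from the affected arm: the other 49 values have sum 35.7 and sum of squares 42 x 0.36 + 7 x 2.25 = 30.87. Their sum of squares about their mean is 30.87 - 35.7²/49 = 30.87 - 26.01 = 4.86. A second value of 3 x ULN would need at least (3 - 35.7/49)² x 49/48 = 5.27, which exceeds 4.86. So exactly one subject is above 3 x ULN at that visit. What the tables cannot show is whether it is the same subject at the next visit. That missing link leaves the range of 1 to 8.

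**5. How special is one arm?** If k affected subjects fell at random into arms of 50, the chance that all share an arm is 2 x C(50,k)/C(100,k): 49% for k = 2, 12% for k = 4, 0.6% for k = 8.

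**6. Both arms affected.** With 4 High starters per arm and the high value alternating between arms by visit, an arm with a high value has maximum 8.0 and mean change 0.13; without one, maximum 1.5 and change 0. High to High is 4 and Normal to Normal 46 throughout. The tables show at least 2 subjects but are the same for 2, 4 or 8.

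**7. A less constructed check.** Simulation with assumed log-normal ALT and k subjects, each with one to three consecutive visits at 3.1 to 10 x ULN. The by-arm maxima alone establish on average 1.01, 1.52, 1.88 and 1.99 subjects for k = 1, 2, 4 and 8. Using n, mean, SD, maximum and the number High together, the tables establish more than 2 subjects in 13% of runs at k = 4 and in 63% at k = 8 (mean 2.8). The bound improves but still falls well short of 8.

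**8. The latest-value rule, if it applies to a retest.** One peak of 8 x ULN is retested at 1.5, and both values are assigned to the same time point. The tables then show maximum 1.5 and maximum change 0 instead of 8.0 and +6.5, that is 0/100 instead of 1/100 above 3 x ULN. The shift cells are identical either way.

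**The case against.** The strongest reply is that the SAP delivers what the protocol names: change from baseline in chemistry, with observed values and shifts, by arm and overall. No passages conflict. No on-treatment threshold is defined, the low/normal/high scheme covers every biochemistry and haematology analyte, and uveitis and ECG are the items given their own handling. All values are listed, so with about 100 subjects a count by hand is a short task. The AE tables also count subjects: "if a subject has multiple occurrences of an AE, the subject will be counted only once for the respective Preferred Term".

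Much of this stands. It makes the point a gap in summary, and cut-offs other than 2 x ULN can only be proposals. It does not close the gap. A hand count from listings is not a planned result, and its threshold would be chosen after the data are seen. AE tables depend on the investigator reporting the elevation and need not match a fixed multiple of ULN. Only the protocol synopsis is available here, so any fuller rules on hepatic monitoring cannot be judged.

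Three stronger readings are tempting and are not supported:

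- *That marked elevations would be hidden or lost.* They would not; SAP 6.4.2 lists every value and flags abnormal ones.
- *That the latest-value rule removes peaks.* It does so only if a repeat is assigned to the same time point as the peak. The SAP is silent on that; if the repeat is kept apart, the peak stays in the tables.
- *That with two arms the tables can never establish more than two subjects.* This is true of the maxima alone. Mean, SD and shift counts can establish more, as step 7 shows.

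**Conclusion.** The point holds as a reporting gap in a named safety outcome. SAP 6.4.2 and 8.1 contain no count of subjects by multiple of ULN or by worst value, and the planned statistics bound that count without giving it. In the constructed example the same tables fit anything from 1/100 to 8/100. That example needs only two distinct baseline values, no within-subject variation and exactly one high value per visit, so it shows that the ambiguity exists, not how large it would be in the trial. The 50/50 split and the number of subjects starting above normal are assumptions; the latter may be small.

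The latest-value point is conditional and secondary. The change is worth making because the remedy is concrete and uses data already collected. Confidence is medium.

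**What to change.** Keep both existing tables. Add to SAP 6.4.2 and 8.1 one Safety Population table, by parent treatment and overall:

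- **Rows:** number and % of subjects by worst post-baseline ALT, and likewise AST, at >2 x ULN (the protocol's entry limit) and at >3, >5 and >10 x ULN (proposed cut-offs, not document figures).
- **Data:** all scheduled and unscheduled post-baseline values, so that the latest-value rule does not apply to this table.
- **Denominator:** for each row, subjects with a post-baseline value who were not already above that threshold at baseline. Show those already above it on a separate line by parent arm. This matters because "baseline is the last non-missing result prior to first dose including the data collected during the parent study" and "Subjects who received RHB-104 will continue to receive RHB-104" (SAP 6.1.2 and 4.2), so for prior RHB-104 subjects the baseline is generally measured after exposure to the drug.
- **Combined row:** ALT or AST >3 x ULN with total bilirubin >2 x ULN from the same sample or within a prespecified window, for example 30 days (a proposal). Without a time link, unrelated rises months apart would count together.

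Confidence intervals are optional. It would also help to state how unscheduled repeats are assigned to time points in the existing tables.

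Cost: SAP wording and one programmed table from ALT, AST and bilirubin already collected, with no new samples or visits. The drawback is one more table that will hold small counts.

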
	
optometrist.
 
 Evidence of any significant hematological, hepatic, renal, cardiac, pulmonary, metabolic, neurological, psychiatric or other disease (e.g. porphyria) that might interfere with subject's ability to safely enter and or complete the study requirements. Clinically significant abnormalities of hematology or biochemistry as confirmed by repeat testing based on investigator's discretion, including but not limited to, elevations greater than 2 times the upper limit of normal of Aspartate Aminotransferase (AST), Alanine Aminotransferase (ALT), or creatinine clearance less than 60 ml/min at screening via estimated Cockcroft-Gault formula: $\text{Creatinine Clearance} = [140 - \text{age in years}] * \text{weight (kg)} / 72 * \text{Serum Creatinine (mg/dl)}$ [multiply estimated rate by 0.85 for women], using actual body weight. QTcF>450ms in males and QTcF>460ms in females, bundle branch block, or major ST or T wave abnormalities that make the assessment of the QT impossible. Females who have a positive pregnancy test or are lactating.
Number of Subjects:	Estimated total: Approximately 100 subjects
Number of Sites:	The study will be conducted at up to 150 sites in the USA, Canada, Israel, Australia, New Zealand, Poland, Bulgaria, Czech Republic, Romania, Slovakia and Serbia

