Table 14.3.1.6	Treatment-Emergent Serious Adverse Events by System Organ Class and Preferred Term: Safety Population
Table 14.3.1.7	Treatment-Emergent Serious Adverse Events by System Organ Class, Preferred Term, and Maximum Relationship to Study Drug: Safety Population
Table 14.3.2.1	Listing of Subjects with Adverse Events that Led to Death: Safety Population
Table 14.3.2.2	Listing Subjects with Treatment-Emergent Serious Adverse Events: Safety Population
Table 14.3.2.3	Listing Subjects with Adverse Events that Led to Study Discontinuation or Study Drug Interruption: Safety Population
Table 14.3.2.4	Listing of Subjects with Treatment-Emergent Adverse Events Related to Study Drug: Safety Population
Table 14.3.2.5	Listing of Deaths: Safety Population
Labs Assessments	
Table 14.3.4.1	Biochemistry Laboratory Data – Observed and Change from Baseline: Safety Population
Table 14.3.4.2	Biochemistry Laboratory Data – Shift from Baseline: Safety Population
Table 14.3.4.3	Hematology Laboratory Data – Observed and Change from Baseline: Safety Population
Table 14.3.4.4	Hematology Laboratory Data – Shift from Baseline: Safety Population
Table 14.3.4.5	Urinalysis Laboratory Data – Observed and Change from Baseline: Safety Population
Table 14.3.4.6.1	Urinalysis Laboratory Data – Shift from Baseline – Numerical Tests: Safety Population
Table 14.3.4.6.2	Urinalysis Laboratory Data – Shift from Baseline – Categorical Tests: Safety Population
Other Safety Assessments	
Table 14.4.1	Vital Signs – Observed and Change from Baseline by Visit: Safety Population
Table 14.4.2	Summary of Uveitis Assessment by Visit: Safety Population

Listings:

Listing Number	Title
Listing 16.2.1.1	Subject Disposition and End of Participation in the Trial: Intent-to-Treat Population
Listing 16.2.1.2	Inclusion and Exclusion Criteria: Intent-to-Treat Population
Listing 16.2.2	Major Protocol Deviations: Intent-to-Treat Population
Listing 16.2.3	Analysis Populations: Intent-to-Treat Population
Listing 16.2.4.1	Demographics and Baseline Disease Characteristics: Intent-to-Treat Population
Listing 16.2.4.2	Crohn's Disease History: Intent-to-Treat Population
Listing 16.2.4.3	Medical History (excluding Crohn's disease): Intent-to-Treat Population

Listing 16.2.4.4	Surgical History of Crohn's disease: Intent-to-Treat Population
Listing 16.2.4.5	Prior Biological Agents Use: Intent-to-Treat Population
Listing 16.2.4.6	Prior Alcohol Consumption and Tobacco Use: Intent-to-Treat Population

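### The latest-value rule for laboratory results, with no worst post-baseline shift table, can understate transient abnormalities in the summary tables; the listings keep them

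*SAP*

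**What the plan says.** SAP 6.4.2 sets the rule for several values at one time point: "If a subject has more than one value at any time point, then the latest non missing value will be used for summarization". It makes no exception for repeat or unscheduled samples.

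The rule reaches the shift tables, because the same section says "Laboratory parameters will also be summarized in shift tables by treatment". Subjects are "classified in a particular category at each post-baseline visit with reference to the same classification at baseline", so the unit is the visit. Continuous biochemistry and hematology parameters "will use the classifications of low, normal, and high relative to normal ranges".

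The section also keeps the individual results. "All values will be presented in the data listings", values outside the normal range are marked there, and "A listing of lab parameter values flagged as abnormal will also be provided".

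In SAP 8.1 the laboratory tables run from 14.3.4.1 to 14.3.4.6.2. They are of two kinds: observed values with change from baseline, and shift from baseline, for example "Biochemistry Laboratory Data – Shift from Baseline: Safety Population". No title refers to a worst post-baseline value or to an abnormality at any time.

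SAP 6.1.2 takes the last non-missing result before the first dose as the laboratory baseline.

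The protocol synopsis mentions repeat blood testing once, among the exclusion criteria: "Clinically significant abnormalities of hematology or biochemistry as confirmed by repeat testing".

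**The concern.** Laboratory samples are often repeated because a result was out of range. Where that is the reason, a latest-value rule can replace an abnormal result with a normal one in the tables, and it cannot do the opposite. A high ALT followed by a normal repeat at the same time point would be counted as normal, and no planned laboratory summary table would show the high value.

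Safety is a stated objective, treatment lasts up to 52 weeks, and shift tables are where a reader looks for counts and percentages of laboratory abnormalities by parent-study group. Listings hold the values but give no numerator, denominator or group comparison.

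The rule also sits oddly beside the SAP's treatment of adverse events, which leans the cautious way. A missing severity counts as severe, a missing relationship counts as related, and events are tabulated at maximum severity (SAP 6.1.3 and 6.4.1).

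**Working it through.** The SAP gives no figure on this point, so there is nothing to reproduce. The check is a reading of the rule, followed by an illustration.

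**Step 1: does the rule cover the shift tables?** Yes. SAP 6.4.2 describes the shift tables as summaries and applies the latest-value rule to summarization without restriction.

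**Step 2: does another planned table keep the abnormal value?** No laboratory table in SAP 8.1 does, judging by the titles. The table layouts are in a separate document that was not available.

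**Step 3: what happens to a repeat sample?** SAP 6.4.2 does not say how repeat or unscheduled samples are assigned to a time point. There are two cases.
- If the repeat is assigned to the visit, it replaces the earlier value in that visit's tables.
- If an unscheduled sample is assigned to no visit, any abnormality it shows enters no by-visit shift table. From week 8 to week 52 the laboratory visits fall at weeks 8, 16, 26, 39 and 52, which leaves gaps of 8, 10, 13 and 13 weeks.

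**Step 4: direction.** If every retest is prompted by an abnormal value, the by-visit count of abnormal results can only stay the same or fall. The count of *shifts* is less simple. Under SAP 6.1.2 a baseline result that was abnormal and then normal on a pre-dose repeat is classed as normal. A later abnormal value in that subject is then a normal-to-abnormal shift, where the earlier baseline value would have made it abnormal-to-abnormal. The baseline rule can therefore add shifts while the post-baseline rule removes them.

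**Step 5: size.** Let
- p = share of subjects whose first value at a visit is abnormal,
- r = share of these retested at the same time point,
- q = share of those retests that are normal.

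The by-visit table shows p × (1 − r × q) instead of p, so the share lost is r × q. The documents give none of the three, so all are assumptions. For 100 subjects (the planned enrollment in SAP 6.1.7, used only for scale) and p = 10%:

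| r | q | Abnormal counted, of 10 | Share lost |
|---|---|---|---|
| 0 | any | 10 × (1 − 0) = 10 | 0% |
| 1 | 0 | 10 × (1 − 0) = 10 | 0% |
| 0.25 | 0.5 | 10 × (1 − 0.125) = 8.75 | 12.5% |
| 0.5 | 0.4 | 10 × (1 − 0.20) = 8.0 | 20% |
| 0.5 | 0.5 | 10 × (1 − 0.25) = 7.5 | 25% |
| 0.8 | 0.6 | 10 × (1 − 0.48) = 5.2 | 48% |
| 0.75 | 0.75 | 10 × (1 − 0.5625) ≈ 4.4 | 56% |

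The share lost does not depend on p. It is zero when nobody is retested at the same time point, or when every retest is still abnormal in the same direction.

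**The case against.** The strongest reply is that the plan keeps the data and that the mechanism is not documented.

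- *The values are not erased.* A reader of the table rule alone might infer that an abnormal first result disappears. It leaves the summary tables only. It remains in the full listing, marked as out of range, and in the listing of abnormal values. With about 100 subjects, reading that listing is feasible. This stands. What the listing lacks is a tabulated rate.
- *On-treatment retesting is not shown.* The repeat testing in the protocol synopsis is an eligibility criterion. It does not establish that retests occur after baseline, how often, or that they fall at the same time point. Visit windows are ±3 or ±7 days, so a later retest need not displace the scheduled value. It also concerns clinically significant abnormalities, whereas the shift tables count any value outside the normal range. A retest rate of 50-80% for every slight excursion has no basis in the documents. This stands, and it rules out saying that abnormalities *are* undercounted. On the other side, the rule itself anticipates several values at one time point.
- *The bias is not strictly one-way.* A reader might infer that the rule always reduces shifts. The baseline definition prevents that conclusion, as step 4 shows.
- *Persistent abnormalities still appear.* Hematology and biochemistry are scheduled at eight post-baseline visits, so an abnormality that lasts is tabulated. Abnormalities reported as adverse events also appear in the adverse event tables. Only a transient result is at risk, and some of those are spurious.
- *Latest value is a legitimate rule.* It is explicit and reproducible, while worst value has an upward bias of its own. This is a good reason to leave the by-visit tables alone. It does not argue against adding a table beside them.

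**Conclusion.** The point holds as a gap in the summary tables. Under SAP 6.4.2 and the table list in SAP 8.1, an abnormal laboratory result followed by a normal repeat at the same time point is tabulated as normal and can be found only in the listings. Transient abnormalities can therefore be understated in the tables.

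The amount cannot be determined from the documents. It is r × q, from 0% with no such retests to 20-48% if 50-80% of abnormal results are retested at the same time point and 40-60% of those retests are normal. More extreme assumptions give more. The 20-48% figure illustrates the formula and is not an estimate for this trial. The documents do not support an established undercount or a fixed direction for net shifts.

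This is an inexpensive improvement to safety reporting. It does not affect the efficacy analyses.

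**What to change.** Keep the by-visit summaries and by-visit shift tables as planned. Add to SAP 6.4.2 and SAP 8.1 one shift table for biochemistry and one for hematology, from baseline to the worst post-baseline value per subject, with repeat and unscheduled samples included. For parameters that can be abnormal in both directions, such as sodium, potassium and white cell count, tabulate the lowest and the highest post-baseline value separately, because a single worst value is otherwise undefined. A sentence on how repeat and unscheduled samples are assigned to visits would also make the by-visit tables reproducible.

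The cost is a few sentences and one or two tables from data already collected. Abnormality rates in the new tables will look slightly less favorable, and an occasional spurious value will be counted. The by-visit tables and the listings beside them let a reader judge those cases.
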